5.2 Secondary Outcomes

- 5.2.1 Toxicities will be evaluated per CTCAE Version 5.0 one month following completion of therapy and then every 3 months thereafter until 25 months from completion of radiation therapy.
- 5.2.2 Patterns of progression will be defined as follows: Local progression will be defined as in field progression (see Section 5.1.1); regional progression will be defined as any new regional lymphadenopathy in the hilum or mediastinum that was not included in the gross tumor volume (GTV); distant progression will be defined as any radiographic or pathologic evidence of disease outside the primary tumor and regional lymph nodes, including subsequent pulmonary parenchymal lesions. Progression-free survival will be evaluated by considering the time from registration to progression of disease or death; those who do not experience either outcome will be censored at date of last visit. Overall survival will be evaluated by considering the time from registration to death from any cause; those who do not die will be censored at date of last visit. Progression will be assessed through CT scans administered immediately following treatment and then every 3 months after that, out to 25 months.

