6.0 Treatment Plan

6.1 Study-Related Activities

Activity	Pre- Study ^a	Prior to First Fraction of RT	At Each Weekly Treatment Visit on RT	1 month after RT completion	Every 3 months after 1 month post-RT scan until 25 months after RT ¹
Informed consent	X				
Demographics	X				
Medical history	X			X	X
Concurrent meds	X				
Physical exam	X			X	X
Vital signs ^g	X			X	X
Height ^d , Weight, ^g	X			X	X
Performance Status ^g	X		X	X	X
Tumor measurements ^e	X			X	X
B-HCG ^b	X				
FDG PET/CT Skull Base to Mid Thigh ^j	X				
MRI Brain with contrasti	X				
CT Chest/Abdomen ^c				X	X
Adverse event evaluation ^f Mandatory target coverage/dose constraint	X	X	X	X	X
compliance ^k				: 121:	

^a Pre-study requirements listed in table must be completed within 12 weeks prior to registration.

^b Serum or urine pregnancy test (women of childbearing potential). This must be completed within one week prior to initiation of radiotherapy for women of childbearing potential. For our purposes postmenopausal women are defined as women over the age of 45 years old with at least 12 months from their date of last menstruation.

^c CT Chest/Abdomen will be with contrast unless the patient has a documented contraindication to IV CT contrast (ie inadequate renal function or anaphylaxis). The scan must include the entire bilateral lungs, liver, and bilateral adrenal glands. CT Chest/Abdomen/Pelvis is also acceptable.

^d Height measured at pre-study only

e See Appendix Q

f See Appendices F and G

g See Appendix L

^h See Appendix C

¹ If MRI is contraindicated, CT Head with contrast is also acceptable.

^j National guidelines indicates a PET scan is good for 3 months (12 weeks).

^k See Appendix N

¹For all follow-up imaging and clinic follow-up time points above, a flexibility window of +/- 8 weeks is allowed.

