8.1.1 Survival Outcomes

Progression-Free Survival is defined as the duration of time from the start of treatment to the time of progression, death, or date of last contact; those lost to follow-up will be censored.

Overall Survival is defined as the duration of time from the start of treatment to date of death or date of last contact; those lost to follow-up will be censored.

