11.2 Analysis of Secondary Objective

- 11.2.1 We will compute the proportion of the sample developing any toxicity of grade 2 or higher over the 25 months, and construct a corresponding 95% confidence interval.
- 11.2.2 We will compute proportions of patients who have experienced local progression by 13 months (1 year following first post-radiotherapy scan) and by 25 months (2 years following first post-radiotherapy scan), and will also compute the same two proportions considering regional progression, distant progression, and any (of the 3 categories) progression. We will construct 95% confidence intervals around these proportions. Those patients for whom we are unable to determine progression status at 1 and 2 years (e.g., because they do not return for the necessary scans, or because they die without evidence of progression) will be left out of these analyses. We will evaluate PFS and OS first using the Kaplan-Meier lifetable method, and will estimate median survival and corresponding 95% CIs; we will also explore simple Cox proportional hazards models of each of these survival outcomes, to examine the predictive influence of variables such as age, gender, ECOG performance status, stage at diagnosis, PTV 7000+6750 volume, and PTV 5750 volume. Patients who are lost to follow-up will be censored at that time in these analyses.

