11.3 Power and Sample Size

11.3.1 Prior studies suggest an average proportion of 0.50 of patients who are free from in-field progression at 2 years following standard radiotherapy alone. ^{4,9} Based on prior reports of dose escalated hypofractionated radiotherapy and our institutional experience using a similar dose fractionation scheme, we hypothesize that HRT will improve 2 year freedom from in-field progression from this 50% to 75%. ^{1,2,22} With a sample size of n=25, we will have 80% power to detect this increase, assuming a one-tailed α of 0.05. We anticipate that approximately 10% -15% of patients recruited will not provide data on our primary outcome at 2 years, so we anticipate recruiting n=30 patients total to allow us to have a total n of 25 for our primary analysis.

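### The PFS censoring dates are not tied to the last scan, so if patients miss CTs but are still seen or contacted, Kaplan-Meier PFS is biased slightly upward

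*Combined protocol and SAP*

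**What the plan says.** Three sections of the combined protocol and SAP set the PFS censoring date.

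- Section 5.2.2 measures PFS from registration: "those who do not experience either outcome will be censored at date of last visit". Overall survival (OS) gets the same censoring date.
- Section 8.1.1 measures PFS from the start of treatment "to the time of progression, death, or date of last contact; those lost to follow-up will be censored".
- Section 11.2.2, on the Kaplan-Meier and Cox analyses, says: "Patients who are lost to follow-up will be censored at that time in these analyses".

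The method of detecting progression is stated in 5.2.2: "Progression will be assessed through CT scans administered immediately following treatment and then every 3 months after that, out to 25 months". The activity table in Section 6.1 marks CT and physical examination together at 1 month after radiotherapy and then in the column headed "Every 3 months after 1 month post-RT scan until 25 months after RT". Its footnote allows 8 weeks either way for both imaging and clinic visits. The weekly visits during radiotherapy carry no CT.

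For the 1- and 2-year progression proportions, Section 11.2.2 leaves out patients whose status cannot be determined, for instance "because they do not return for the necessary scans". It has no corresponding rule for PFS.

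**The concern.** A visit or contact shows that a patient is alive. Without a scan it does not show that the tumour is controlled. A last-visit or last-contact date therefore suits OS, but for PFS it can keep a patient in the risk set over a period in which progression could not have been seen. Section 11.2.2 illustrates the mismatch: a patient who stops attending for CT is treated as unknown in the progression proportions, yet counts as progression-free in the PFS curve up to the last visit or contact.

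The direction of the error is known. For the same events, moving censoring dates later enlarges later risk sets and adds no events, so the Kaplan-Meier curve stays the same or rises. PFS is a named secondary result (Section 2.2.2), and the error would favour the regimen.

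**Working it through.** **1. The plan's own figures.** The documents give no PFS rate, event count or PFS power; the only calculation to reproduce is the primary one (Section 11.3: 0.50 against 0.75, one-sided 0.05, 80% power).
- n = (1.645 + 0.842)² × 0.5 × 0.5 / 0.25² = 24.7, so 25. Power at n = 25 is 80.4%.
- 25/0.90 = 27.8, so 28; 25/0.85 = 29.4, so 30. This matches the planned 30.

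None of these figures uses the PFS censoring date, so they stand.

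**2. When the dates coincide and when they separate.** If the Section 6.1 schedule is kept, the last follow-up visit has a CT, the gap is zero and so is the bias. The dates separate in four ways:
- a scan is missed while the patient is still seen;
- the two windows pull scan and visit apart, by at most 8 + 8 = 16 weeks, about 3.7 months;
- the last visit is a weekly radiotherapy visit;
- the last contact is not a visit, which matters only under the 8.1.1 wording.

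**3. Size if patients stop scanning but stay in contact to month 25.** Assumptions not in the documents: exponential PFS with median 9, 12 or 18 months; 75% of first events are progressions; median survival after progression 9 months; scans at months 1, 4, ..., 25; stopping after a randomly chosen scan. The share stopping is taken from Section 11.3 ("We anticipate that approximately 10% -15% of patients recruited will not provide data on our primary outcome at 2 years"). There were 400,000 simulated patients per scenario. The Kaplan-Meier estimate is read just before month 25 and compared with full scanning.

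| Median PFS (months) | Full scanning | Contact, 10% stop | Contact, 15% stop | Contact, 30% stop |
|---|---|---|---|---|
| 9 | 17.0-17.2% | 17.9% | 18.5% | 19.9% |
| 12 | 26.6% | 27.5% | 27.9% | 29.2% |
| 18 | 41.2-41.5% | 42.0% | 42.6% | 43.9% |

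The excess is 0.8 to 1.3 points at 10-15% and about 2.5 points at 30%. The 30% column is a stress case with no basis in the documents. Estimated median PFS at 10-15% was 10, 13 and 19 months both with full scanning and with last-contact censoring. The estimates exceed the true medians because progression is recorded at the next scan.

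**4. Size by gap between last scan and last contact.** A second simulation used 200,000 patients per scenario, with independent exponential times and assumed medians of 12, 18 or 24 months to progression and 24, 30 or 36 months to death. PFS is read 24 months after radiotherapy, with 10-15% stopping.

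| Gap (months) | Above last-scan censoring (points) | Above full scanning (points) |
|---|---|---|
| 0 | 0 | 0 |
| 2 | 0.1-0.2 | 0 |
| 3.7 | 0.3-0.7 | 0.2-0.4 |
| 6 | 0.6-1.3 | 0.4-0.8 |
| 12 | 1.1-2.1 | 0.8-1.3 |

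The middle column is the larger because the last-scan comparator still counts later deaths and so errs low itself. Median PFS moved by 0 to 0.3 months.

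**5. Effect of the remedy.** Under the assumptions of step 3 at 10-15% stopping, the error against full scanning is:
- last contact: +0.8 to +1.3 points;
- last scan, counting every later death: -0.7 to -1.6 points;
- last scan, with patients who die after two or more consecutive missed scans also censored at the last scan: -0.3 to -0.6 points.

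**6. Sampling error for scale.** With 30 patients and 2-year PFS near 27%, the standard error is √(0.27 × 0.73 / 30) = 0.081, about 8 points.

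**The case against.** The strongest reply is that Section 5.2.2 already does nearly the right thing: with CT at every follow-up visit, last visit means last scan unless a scan is missed or displaced. That stands. A reader might infer that the PFS date is wrong whichever section prevails, but the documents do not support this. Settling on last visit would remove much of the exposure, though not the case of a visit without its scan.

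A reader might also take the telephone call in Section 6.4 as a substitute for follow-up visits up to month 25. It is not. The call covers the 30-day window after radiotherapy and concerns vital status and adverse events. Nor is the extreme patient, scanned once at month 1 and then only contacted until month 25, a measure of size; nothing suggests that such patients would be common.

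The 10-15% figure is close to a ceiling. Section 11.3 does not say that these patients stay in contact. Some will have died without recorded progression (Section 11.2.2 gives this as a reason for unknown status), and for others scans and contact will end together. Neither group gains unscanned event-free time.

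Finally, Section 11.2.2 names the median as the PFS summary, not a 2-year rate; Section 11.0 calls the analyses beyond the primary aim largely descriptive; and the shift is well inside sampling error. All of this stands and limits the weight of the point. It does not remove a stated rule that can err only in the regimen's favour.

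**Conclusion.** The point holds in a limited form. None of the three sections ties PFS censoring to the last scan, and no other section corrects this. The bias is conditional on scans being missed or displaced while the patient is still seen or contacted; its direction is then upward, and 8.1.1 is the most exposed.

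The size is small: about 1 point in 2-year PFS if all of the 10-15% stop scanning but remain in contact, and 0.1 to 0.7 points, against last-scan censoring, for gaps of 2 to 3.7 months. Median PFS is essentially unchanged. These figures rest on assumed progression and death rates, since the documents give none for this trial. No decision in the plan depends on PFS. The case for acting is that the direction is known, the correction is cheap, and the same sections need editing anyway because they disagree on time origin (registration or start of treatment) and on last visit or last contact.

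**What to change.** When 5.2.2, 8.1.1 and 11.2.2 are reconciled:

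1. Choose one time origin for PFS and OS.
2. For patients without progression or death, censor PFS at the date of the last CT that showed no progression. Keep last visit or contact as the censoring date for OS only.
3. State before analysis how deaths after missed scans are handled. One option is to censor at the last scan when death follows two or more consecutive missed scans, with a sensitivity analysis that counts all deaths. Some such rule is needed because last-scan censoring that counts every later death errs low by about as much as the present wording errs high.

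The cost is about a sentence in each section. No new data are needed: scan dates are already recorded on Appendix I. The downside is that reported PFS may be slightly less favourable, and under the example rule a few late deaths leave the main PFS analysis, which is why the sensitivity analysis should accompany it.

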6.0 Treatment Plan

6.1 Study-Related Activities

Activity	Pre- Study ^a	Prior to First Fraction of RT	At Each Weekly Treatment Visit on RT	1 month after RT completion	Every 3 months after 1 month post-RT scan until 25 months after RT ¹
Informed consent	X				
Demographics	X				
Medical history	X			X	X
Concurrent meds	X				
Physical exam	X			X	X
Vital signs ^g	X			X	X
Height ^d , Weight, ^g	X			X	X
Performance Status ^g	X		X	X	X
Tumor measurements ^e	X			X	X
B-HCG ^b	X				
FDG PET/CT Skull Base to Mid Thigh ^j	X				
MRI Brain with contrasti	X				
CT Chest/Abdomen ^c				X	X
Adverse event evaluation ^f Mandatory target coverage/dose constraint	X	X	X	X	X
compliance ^k				: 121:	

^a Pre-study requirements listed in table must be completed within 12 weeks prior to registration.

^b Serum or urine pregnancy test (women of childbearing potential). This must be completed within one week prior to initiation of radiotherapy for women of childbearing potential. For our purposes postmenopausal women are defined as women over the age of 45 years old with at least 12 months from their date of last menstruation.

^c CT Chest/Abdomen will be with contrast unless the patient has a documented contraindication to IV CT contrast (ie inadequate renal function or anaphylaxis). The scan must include the entire bilateral lungs, liver, and bilateral adrenal glands. CT Chest/Abdomen/Pelvis is also acceptable.

^d Height measured at pre-study only

e See Appendix Q

f See Appendices F and G

g See Appendix L

^h See Appendix C

¹ If MRI is contraindicated, CT Head with contrast is also acceptable.

^j National guidelines indicates a PET scan is good for 3 months (12 weeks).

^k See Appendix N

¹For all follow-up imaging and clinic follow-up time points above, a flexibility window of +/- 8 weeks is allowed.

6.1.1 Radiation Therapy

Hypofractionated radiation therapy will be delivered to all patients. The prescribed dose will be 70 Gy in 25 fractions

- 1. Technical Factors and Radiation Planning
 - a. Radiation Dose Selection
 - i. The radiation dose for the high dose PTV was selected based on previous clinical experience with 70.2 Gy in 26 fractions, and decreasing the treatment course by one fraction, leading to a **high dose of 70 Gy in 25 fractions.** As this dose is likely not necessary for control of microscopic disease treated in the clinical target volume (CTV), a **lower dose CTV will be treated to 57.5 Gy in 25 fractions.** This lower dose was selected based on BED and EQ2D calculations, which can be used to compare doses using non-standard (ie non 1.8-2 Gy) fraction sizes (see Table 1).

ii.

Table 1. COMPARISON BED and EQD2 for Dose Fractionation Schemes				
Dose / Fractions	BED ₁₀ Gy (Tumor)	BED ₃ Gy (Normal Tissue)	EQD2 ₁₀ Gy (Tumor)	EQD23 Gy 2 (Normal Tissue)
60 Gy / 30 fx (SoC)	72	100	60	60
66 Gy / 30 fx	80.52	114.4	67.1	68.84
70.2 Gy / 26 fx	89.15	133.38	74.3	80.03
58.5 Gy / 26 fx	71.66	102.38	59.72	61.43
66 Gy / 24 fx	84.15	126.5	70.13	75.9
70 Gy / 25 fx	89.6	135.33	74.67	81.2
67.5 Gy / 25 fx	85.73	128.25	71.44	76.95
57.5 Gy / 25 fx	70.72	101.58	58.94	60.95

b. CT Simulation

- i. All patients will undergo CT simulation of the chest. The use of intravenous contrast with the CT simulation is not mandatory.
- ii. 4D-CT will be obtained for motion management. The use of abdominal compression or respiratory gating is encouraged.
- iii. Immobilization will be done with a customized vacuum sealed bag.
- c. Target Volume Definitions:

WFBCCC # 62220

- i. GTV = gross tumor (both primary and lymph nodes) on CT simulation. Lymph nodes > 1 cm in short axis diameter or with an SUV > 3 are considered to be involved unless proven negative by biopsy.
- ii. iGTV = GTV accounting for tumor motion on all phases of 4D CT
- iii. CTV 7000 = iGTV with no expansion
- iv. CTV_5750 = iGTV uniformly expanded by 5mm
 - 1. CTV_5750 can be excluded from normal structures without radiographic evidence of invasion (for example≤ vertebral bodies, chest wall, or ribs)
 - 2. CTV_5750 should not be excluded from the trachea, esophagus, proximal bronchial tree, or intrathoracic cardiovascular structures
- v. PTV_7000 = CTV_7000 uniformly expanded 5mm minus Esophagus_PRV, PBT_PRV, and Brachial Plexus PRV (if applicable)
- vi. PTV_5750 = CTV_5750 uniformly expanded by 5mm
- vii. PTV 6750 = PTV 7000 minus PBT 1cm
 - PTV_6750 will only be delineated in cases where dose constraints for the PBT cannot be met
- d. Organs at Risk to be contoured
 - i. For all patients
 - 1. Bilateral lungs
 - 2. Spinal cord (5 cm above and below the PTV)
 - 3. Aorta (5 cm above and below the PTV)
 - 4. Esophagus (entire length)
 - 5. Esophagus PRV = Esophagus plus 5mm uniform expansion
 - 6. Heart (including the pericardial sac)
 - 7. Trachea/proximal bronchial tree
 - a. 5 cm superior to the PTV to the end of all main lobar bronchi
 - 8. PBT_PRV = trachea and proximal bronchial tree plus 5mm uniform expansion
 - ii. For patients with the PTV within 2 cm of the organ at risk*
 - 1. Brachial plexus
 - a. Only the major trunks of the brachial plexus need to be contoured
 - b. Left and right brachial plexuses should be contoured separately with generation of separate Brachial_Plexus_PRVs if the PTV is within 2 cm of both brachial plexuses
 - 2. Brachial_Plexus_PRV = Brachial plexus plus 5mm uniform expansion
 - 3. Chest wall (3 cm superior and inferior to the PTV)
 - 4. Ribs
 - 5. Stomach
 - 6. Liver
 - * if non-coplanar beams or arcs are used then all organs at risk must be contoured For patients who cannot meet PBT dose constraints
 - 1. PBT_1cm = trachea and proximal bronchial tree plus 1 cm uniform expansion iv.
 - Target Coverage Requirements
 - i. Mandatory
 - 1. 95% of PTV 5750 to at least 95% of prescription (54.63 Gy)
 - 2. 99% of PTV 5750 to at least 90% of prescription (51.75 Gy)
 - ii. Ideal

iii.

- 1. 95% of PTV 7000/6750 to at least 95% of prescription (66.5 Gy/64.13 Gy)
- 2. 100% of PTV 7000/6750 to at least 95% of prescription (66.5 Gy/64.13 Gy)
- 3. 95% of PTV_7000/6750 to at least 100% of prescription (70 Gy/67.5 Gy)
- 4. 99% of PTV 7000/6750 to at least 90% of prescription (63 Gy/60/75 Gy)
- 5. 100% of PTV 5750 to at least 95% of prescription (54.63 Gy)

- f. Organ at Risk Constraints
 - i. Mandatory
 - 1. Spinal Cord: $D0.03 \text{ cm}^3 < 45 \text{ Gy}$
 - 2. Esophagus: $D0.03 \text{ cm}^3 < 73.5 \text{ Gy}$;
 - 3. Lungs-GTV: V20 Gy \leq 35%;
 - 4. Proximal Bronchial Tree: D0.03 cm 3 < 73.5 Gy; D3 cm 3 < 66.25
 - 5. Heart D100% < 30 Gy
 - 6. Stomach: $D0.03 \text{ cm}^3 < 60 \text{ Gy}$
 - 7. Liver: Mean dose < 30 Gy; at least 700 cm³ of normal liver to < 15 Gy
 - 8. Maximum physical dose < 115% of high dose prescription
 - a. PTV_7000: maximum physical dose < 80.50 Gy
 - b. PTV 6750: maximum physical dose < 77.63 Gy
 - ii. Ideal
 - 1. Lungs-GTV: V40 Gy < 10%; V30 Gy < 15%; V20 Gy < 30%; V10 Gy < 60%; mean dose < 20 Gy
 - 2. Proximal bronchial tree: Gy; D15% < 60 Gy
 - 3. Esophagus: Mean dose < 34 Gy; D10 cm³ < 60 Gy; D30% < 55 Gy
 - 4. Aorta: $D0.03 \text{ cm}^3 < 76 \text{ Gy}$; $D10 \text{ cm}^3 < 60 \text{ Gy}$
 - 5. Heart: Mean dose < 30 Gy; D25% < 50Gy; V45Gy < 30%; D0.03cm³ < 73.5Gy
 - 6. Brachial plexus: D0.03cm³ < 60 Gy
 - 7. Stomach: $D0.03 \text{ cm}^3 < 58 \text{ Gy}$; $V50 \text{ Gy} < 5 \text{ cm}^3$; $V45 \text{ Gy} < 75 \text{ cm}^3$
 - 8. Liver: Mean dose < 28 Gy
 - 9. Chest Wall: $V30 \text{ Gy} < 70 \text{ cm}^3$
 - 10. Ribs: $D0.03 \text{ cm}^3 < 57 \text{ Gy}$
 - 11. Maximum dose < 108% of high dose prescription
 - a. PTV 7000: maximum physical dose < 75.6 Gy
 - b. PTV 6750: maximum physical dose < 72.9 Gy
- g. Radiation Therapy prescription and planning
 - Radiation prescription
 - 1. A simultaneous integrated boost will be used to treat all PTVs
 - 2. PTV 7000 = 70.00 Gy in 25 fractions (2.80 Gy per fraction)
 - a. $PTV_6750 = 67.5$ Gy in 25 fractions (2.70 Gy per fraction)
 - 3. $PTV_5750 = 57.50$ Gy in 25 fractions (2.30 Gy per fraction)
 - ii. 3D-CRT, static IMRT, or VMAT plans are acceptable
 - 1. IMRT or VMAT are strongly preferred
 - iii. Heterogeneity corrections will be used for all dose calculations
 - iv. At least 95% of PTV_5750 must be covered by at least 95% of the prescription dose for that PTV. If mandatory dose constraints to organs at risk are unable to be met, ideal target coverage requirements may be compromised at the discretion of the treating physician.
 - v. Ideally no more than 1cm³ of normal tissue outside the PTV 5750 may receive > 62.1Gy
 - vi. Circumferential high dose irradiation (70 Gy or higher) of the trachea, bronchus, and esophagus should be avoided
- h. Radiation Therapy Delivery
 - i. Radiation therapy will be delivered once daily, 5 days per week, Monday-Friday.
 - 1. In cases where Radiation Oncology clinic is closed, the patient may receive only 4 fractions per week at the discretion of the treating radiation oncologist.
 - 2. Treatment breaks are allowable per the discretion of the treating radiation oncologist.
 - ii. Daily image guidance with cone beam CT is recommended.

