Various hypofractionated radiotherapy (HRT) regimens have been reported for the management of patients with early-stage NSCLC not amenable to surgery or SBRT, HRT is commonly implemented, but the optimal dose schedule has not been established. Selection of HRT dose has been informed by studies of HRT/stereotactic body radiotherapy (SBRT) which have established a direct correlation between BED and tumor control. 17,26 Generally speaking, RT doses with BED₁₀ > 100 results in significantly improved disease control when compared to doses with BED₁₀ < 100. For this reason, efforts to deliver various regimens of HRT that reach or approach a BED₁₀ of 100 Gy are of interest. A study conducted by the Cancer and Leukemia Group B (CALGB) 39904 protocol evaluated various HRT regimens to a total dose of 70 Gy in 17-29 fractions without concurrent chemotherapy for early stage T1-T2N0 NSCLC. In this Phase I study, disease control was favorable and no dose-limiting toxicity was observed.

For patients with NSCLC not amenable to SBRT, surgery or concurrent chemoradiotherapy, a commonly utilized HRT fractionation at our institution is 70.2 Gy in 26 fractions. This regimen has a BED $_{10}$ of 89.15 Gy. Recent data from our institution show that this fractionation results in favorable disease control and toxicity profiles. In our cohort, which included stage II patients and those with hilar (N1) nodal involvement, 96% were treated with 70.2 Gy in 26 fractions. The 3 year cumulative incidence of locoregional failure (including in untreated regional lymph nodes) was 32%, and only 2 (4%) of patients developed CTCAE version 4.0 Grade 3 radiation pneumonitis after treatment. No instances of Grade 3+ esophagitis occurred. Based on these data, a similar dose fractionation scheme of 70 Gy in 25 fractions (BED $_{10}$ = 89.6 Gy) is likely to have a 2 year local control rate of approximately 70%. In cases where PBT dose constraints cannot be met, the dose to the PTV within 1 cm of the

PBT will be reduced slightly to 67.5 Gy in 25 fractions (BED₁₀ = 85.73 Gy, BED₃ = 128.25 Gy) to reduce the risk of serious toxicity. A similar dose (66 Gy in 24 fractions, BED₁₀ = 84.15 Gy, BED₃ = 126.5 Gy) has been previously reported to be well tolerated with concurrent low dose daily cisplatin.⁹

Selection of Dose Constraints for the Proximal Bronchial Tree, Esophagus, and Heart

Proximal Bronchial Tree

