We plan to decrease bronchial toxicity risk in multiple ways. First, we will reduce the high dose level for the target area in close proximity to the PBT when dose constraints cannot be met. For these patients, a high dose level of 67.5 Gy in 25 fractions will be prescribed, which is nearly biologically equivalent to 66 Gy in 24 fractions, which has been reported to be safe when used in patients with Stage III NSCLC with daily cisplatin. Second, during construction of the RT plan, any overlapping proximal bronchial tree plus a 5mm uniform expansion (planning organ at risk volume or PRV) will be excluded from the high dose PTV. Second, we will provide dose constraints to bronchial structures (mandatory for maximal dose, and ideal for volumetric constraints) in a similar fashion to RTOG 0813. Finally, we will limit the maximum dose in the entire plan to no more than 115%, unlike the Nordic HILUS study, further reducing the risk of very high doses of radiation being delivered to the proximal bronchial tree due to intrafractional motion.

Esophagus

As with the proximal bronchial tree, late esophageal toxicity is of concern in high dose radiotherapy to the mediastinum and centrally located lung tumors. In RTOG 0813, esophagus adjacent to the target was limited to 105% of the prescription dose. They noted minimal late esophageal toxicity with doses up to 60 Gy in 5 fractions³ Additionally, in Alliance/CALGB 31102, the esophagus was limited to a maximal dose of 105% of the prescription, and a V55 Gy of under 30%, with no reported late Grade 3 or higher toxicity.³⁰ Furthermore, a recent normal tissue complication model of the esophagus developed based on patients treated with hypofractionated radiotherapy reported a 5% late high grade esophageal complication rate with a maximal EQD2₃ dose of 113.3 Gy.¹⁰ Based on these data, we will plan for mandatory esophagus constraints of 73.5 Gy (105% of prescription, EQD2₃ = 87.3 Gy)

and a V55 Gy under 30%. As with the bronchial tree, the esophagus plus a 5mm uniform expansion will be excluded from the high dose target volume.

Heart

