Appendix E: BED Calculations for Dose Levels and Constraints

$$BED = d(n)(1 + d/(\alpha/\beta))$$

- Where:
 - BED = Biologic Effective Dose at a given alpha/beta ratio
 - d = dose per fraction
 - n = number of fractions
 - α/β = alpha/beta ratio

$$EQD2 = BED/(1 + (2/\alpha/\beta))$$

- Where:
 - EQD2 = Equivalent dose in 2 Gy fractions

BED and EQD2 Calculations									
Parameter	Total Dose (Gy)	Dose per fraction (Gy)	Number of Fractions	BED ₁₀ (tumor)	BED ₃ (normal tissue)	EQD2 ₁₀ (tumor)	EQD2 ₃ (normal tissue)		
Standard Therapy	60	2	30	72	100	60	60		
Prior Institutional HRT	70.2	2.7	26	89.15	133.38	74.3	80.03		
Prior HRT with Low Dose Cisplatin	66	2.75	66	84.15	126.5	70.13	75.9		
High Dose PTV	70	2.8	25	89.6	135.33	74.67	81.2		
High Dose PTV (bronchial invasion)	67.5	2.7	25	85.73	128.25	71.44	76.95		
Low Dose PTV	57.5	2.3	25	70.72	101.58	58.94	60.95		
Volumetric PBT Constraint	66.25	2.65	25	83.81	124.77	69.84	74.86		
Brachial Plexus Constraint*	60	2.4	25	74.4	132	62	66		

^{*} α/β of 2 used for normal tissue calculations for nervous system

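### Section 6.1.1 puts the reduced 67.5 Gy dose on target more than 1 cm from the airway; the dose rationale in section 1.0 puts it on target within 1 cm

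*Combined protocol and SAP*

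**What the plan says.** The operative rule is in section 6.1.1, Target Volume Definitions.

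- Item c.v sets the high-dose volume: "PTV_7000 = CTV_7000 uniformly expanded 5mm minus Esophagus_PRV, PBT_PRV, and Brachial Plexus PRV". PBT_PRV is the airway plus 5 mm, so the 70 Gy volume already stops 5 mm short of the airway.
- Item c.vii sets the reduced volume: "PTV 6750 = PTV 7000 minus PBT 1cm". PBT_1cm, in the list of organs at risk, is the trachea and proximal bronchial tree expanded by 1 cm.
- The trigger follows: "PTV_6750 will only be delineated in cases where dose constraints for the PBT cannot be met".
- Item g prescribes 70 Gy to PTV_7000, 67.5 Gy to PTV_6750 and 57.5 Gy to PTV_5750, each in 25 fractions.

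The rationale is in section 1.0. Selection of HRT Dose has one sentence broken across a page: "In cases where PBT dose constraints cannot be met, the dose to the PTV within 1 cm of the", continuing "PBT will be reduced slightly to 67.5 Gy in 25 fractions". The Proximal Bronchial Tree subsection gives the same direction but no distance: "we will reduce the high dose level for the target area in close proximity to the PBT when dose constraints cannot be met". It then adds: "For these patients, a high dose level of 67.5 Gy in 25 fractions will be prescribed". Appendix E lists 67.5 Gy in a row of its own, headed "High Dose PTV (bronchial invasion").

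**The concern.** The rule and its rationale send 67.5 Gy to opposite sides of the 1 cm line. The rule applies to patients whose tumour is close enough to the airway that its limits cannot be met. They are a natural part of this population: ultracentral Stage IB patients qualify because gross tumour lies within 1 cm of the proximal bronchial tree.

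The band between 5 and 10 mm from the airway can contain gross disease, because CTV_7000 is the iGTV with no expansion. Section 6.1.1 chose 57.5 Gy for microscopic disease. The contour line therefore decides whether the planning aim in that band is 57.5, 67.5 or 70 Gy, in a trial whose primary endpoint is in-field control and whose halting rule counts Grade 4 or 5 bronchial events. A planner who follows the formula and one who follows the rationale would plan the same patient differently.

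**Working it through.** **Inputs.** The volume definitions and doses come from section 6.1.1; BED = D(1 + d/(α/β)) comes from Appendix E, with 25 fractions.

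**Reproducing the plan's figures.**
- 70 Gy: 70 × (1 + 2.8/10) = 89.60; BED3 = 135.33.
- 67.5 Gy: 67.5 × (1 + 2.7/10) = 85.725, stated as 85.73; BED3 = 128.25.
- 57.5 Gy: 57.5 × (1 + 2.3/10) = 70.725, stated as 70.72; BED3 = 101.58.

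All agree with Table 1 and Appendix E.

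**Which region gets 67.5 Gy.** Let x be the distance from the airway.
- PTV_7000 is target with x > 5 mm.
- PBT_1cm is x ≤ 10 mm.
- Item c.vii as written: PTV_7000 minus PBT_1cm = target with x > 10 mm.
- Selection of HRT Dose: PTV_7000 intersected with PBT_1cm = target with 5 < x ≤ 10 mm.

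The intersection of the last two sets is empty. The subtraction is not an extraction fault: it is a written word, and item c.v uses it in the same sense.

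**Prescription by region in patients who trigger the rule.** PTV_5750 is built from the iGTV with larger margins and is not cropped at the airway, so it supplies 57.5 Gy wherever the high-dose volume is removed.

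| Interpretation | 5–10 mm band | Beyond 10 mm |
|---|---|---|
| Rationale in section 1.0 | 67.5 Gy | 70 Gy |
| c.vii, PTV_6750 replaces PTV_7000 | 57.5 Gy | 67.5 Gy |
| c.vii, both volumes kept | 70 Gy | 70 and 67.5 Gy |

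Neither way of applying c.vii gives the section 1.0 result.

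**Size under replacement.**
- Band, physical dose: 57.5 − 67.5 = −10 Gy; 10/67.5 = 14.8% lower.
- Band, BED10: 85.725 − 70.725 = 15.0 Gy; 15.0/85.725 = 17.5% lower.
- Beyond 10 mm, BED10: 89.60 − 85.725 = 3.875 Gy; 3.875/89.60 = 4.3% lower.

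The 17.5% compares prescriptions. The band lies beside a 67.5 Gy volume, so its delivered dose would fall between the two levels. The documents give no dose for it; the following mean doses are assumptions.

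| Assumed mean dose in band | BED10 | Against 85.725 |
|---|---|---|
| 57.5 Gy (prescription only) | 70.725 | −17.5% |
| 60 Gy | 74.40 | −13.2% |
| 62.5 Gy | 78.125 | −8.9% |
| 65 Gy | 81.90 | −4.5% |
| 67.5 Gy | 85.725 | 0% |

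**Size if both volumes are kept.** The band stays at 70 Gy instead of 67.5 Gy: 2.5/67.5 = 3.7% higher, with BED3 135.33 instead of 128.25. No step-down then occurs where section 1.0 wants it.

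**The case against.** The strongest reply is that section 6.1.1 can be carried out as it stands: crop the high-dose target 1 cm from the airway and prescribe 67.5 Gy to what is left. Several features support this. Coverage goals are written for PTV_7000 and PTV_6750 as a pair with paired doses. Item g nests PTV_6750 under PTV_7000. The 115% maximum has one value for each level (80.50 and 77.63 Gy), and section 1.0 describes that maximum as applying to the entire plan. The Proximal Bronchial Tree subsection speaks of a single high dose level for these patients, and Appendix E lists 67.5 Gy as an alternative high-dose PTV. On this view the only discordant text is one background sentence, and cropping spares the airway more than that sentence would.

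Much of this stands. Replacement is the likelier reading of c.vii. Keeping both volumes is the weaker one, since it gives the same distant target two prescriptions. The documents do not show which text is the error.

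The reply also limits the harm correctly. The airway dose limits are the same under every reading. High-dose coverage is only an ideal goal and may be compromised at the treating physician's discretion when mandatory organ limits fail. The mandatory floor of 54.63 Gy to 95% of PTV_5750 does not change. Target within 5 mm of the airway is already at 57.5 Gy by design. The 62.1 Gy restriction applies only to normal tissue outside PTV_5750, so the band may receive more than 57.5 Gy.

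What the reply does not do is remove the conflict. Replacement still contradicts Selection of HRT Dose twice: the band is prescribed 57.5 Gy rather than 67.5 Gy, and the distant target 67.5 Gy rather than 70 Gy.

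**Conclusion.** The inconsistency is real and sits in a dose-prescription rule, so it should be fixed. As written, c.vii and the section 1.0 rationale give 67.5 Gy to regions with no overlap, and no other text reconciles them. Under the likelier reading the band's prescription is 10 Gy below what the rationale states, a BED10 deficit of at most 17.5%. The delivered deficit could lie anywhere from 0 to 17.5%, depending on a dose gradient that the documents do not describe.

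A reader might infer three stronger things.

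- **That gross tumour beside the airway will be underdosed by 17.5% and the primary endpoint compromised.** The documents do not support this: the figure compares prescriptions, the mandatory floor is unchanged, and nothing says how many patients will trigger PTV_6750.
- **That the airway is left unprotected.** Its limits bind under every reading.
- **That the subtraction is a proven slip for an intersection.** The surrounding text leans towards deliberate replacement, so only the sponsor can settle it.

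Sample size and the primary test do not depend on this point.

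**What to change.** The sponsor should state which dose arrangement is intended and make the texts agree.

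- **(a) If Selection of HRT Dose is right:** in c.vii define PTV_6750 as PTV_7000 intersected with PBT_1cm, and state that in these patients 70 Gy is kept for PTV_7000 minus PBT_1cm. The two volumes are then disjoint and add up to the full high-dose target.
- **(b) If 67.5 Gy is meant to replace 70 Gy for the whole high-dose target, cropped 1 cm from the airway:** say so in c.vii and correct the sentence in Selection of HRT Dose.

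Either choice gives the combined PTV_7000 and PTV_6750 volume covariate in section 11.2 a clear meaning. Under (a) the two parts sum to the whole; under (b) one term is zero.

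In both cases, state which PBT limits trigger PTV_6750, since the trigger does not name them. Whether the PBT D3 cm³ limit of 66.25 Gy and the esophagus V55/D30% limit are mandatory or ideal should be raised separately as clarifications; this point does not rest on them.

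The cost is one contour line or one background sentence, plus a sentence or two of clarification. No procedure is added, and the sample size and analysis stay as they are.
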